Table 5-1 provides a summary of the sample size requirements based on the three study aims. Although we strive to retain all subjects, the sample size will be adjusted to account for a possible 10% loss to follow-up. This is a reasonable expectation. [name], when at Ohio State, had a retention rate of 98% in his Study of Theories about Myopia Progression clinical trial, and other clinical vision studies conducted at the University of Houston have retention rates exceeding 90%. Likewise, [name] experiences at Ohio State with ACHIEVE (OSU clinic saw 100% of subjects for final visit) and the Contact Lens and Myopia Progression trial (100% of subjects at final visit) indicate that a 10% loss to follow-up is an acceptable assumption. Using the maximum sample size from Table 5-1 (n=267) and adjusting for 10% loss to follow-up gives a **total sample required of 294** (98 children assigned to each treatment group).

Table 5-1: Total sample size required at 80% power in the Soft Bifocal Contact Lens Myopia Control Study

| Aim | Total sample |
|----------------------|--------------|
| Specific Aim 1 | |
| 50% treatment effect | 72 |
| 40% treatment effect | 120 |
| 30% treatment effect | 186 |
| Specific Aim 2 | 123 |
| Specific Aim 3 | 267 |

Chapter 6: Timeline

During the first six months of funding, preparation for the trial will begin. The DSMC will meet as early as possible (after preparation of study forms and DSMC binders) in order to finalize the protocol. Once the protocol is finalized, certification of examiners will begin at the FIG meeting, both near the end of the initial six-month period.

Recruitment will begin at the beginning of month seven and continue for 15 months. All follow-up visits will begin within one week of the first subject visit. The last one-year, two-year, and three-year visits are expected to be complete within one month of the anniversary date of the last subject enrolled.

The DSMC will meet annually, after recruitment and each year of follow-up is complete and the data are analyzed. FIG meetings will be held after each DSMC meeting in order to update protocols, motivate investigators, and discuss problems encountered. Writing groups will also meet during the FIG meetings.

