A baseline manuscript describing the sample, methods, and vision of subjects fit with the +2.50 D add for inclusion criteria will be written when enrollment is complete. When 75% of the subjects have completed the trial, a draft of the primary outcome manuscript will be written. The draft will be shared with the DSMC for approval. When the study is complete, data will be finalized, the entire study group will provide comment prior to submission, and the DSMC will provide final approval. The complete study timeline is shown in Figure 6-1.

Figure 6-1: Timeline for conduct of the Soft Bifocal Contact Lens Myopia Control Study.

| Years | Year 1 | | | | Year 2 | | | | Year 3 | | | | Year 4 | | | | Year 5 | | | |
|-----------------|--------|-----|-----|-------|--------|-------|-------|-------|--------|-------|-------|-------|--------|-------|-------|-------|--------|-------|-------|-------|
| Months | 1-3 | 4-6 | 7-9 | 10-12 | 13-15 | 16-18 | 19-21 | 22-24 | 25-27 | 28-30 | 31-33 | 34-36 | 37-39 | 40-42 | 43-45 | 46-48 | 49-51 | 52-54 | 55-57 | 58-60 |
| Preparation | | | | | | | | | | | | | | | | | | | | |
| Certification | | | | | | | | | | | | | | | | | | | | |
| Recruitment | | | | | | | | | | | | | | | | | | | | |
| Follow-up | | | | | | | | | | | | | | | | | | | | |
| Data analysis | | | | | | | | | | | | | | | | | | | | |
| DSMC | | | | | | | | | | | | | | | | | | | | |
| FIG meetings | | | | | | | | | | | | | | | | | | | | |
| Manuscript prep | | | | | | | | | | | | | | | | | | | | |

Milestone events throughout the study will be scheduled according to the first day of funding. Table 6-2 lists those dates in order to help with goal setting and planning.

Table 6-2: An April 1, 2014 funding date initiates the following events.

| Month | Event |
|-------------------|---|
| April 2014 | Entry of the clinic trial into clinicaltrial.gov |
| April - July 2014 | MOP and forms drafts |
| June 2014 | DSMC suggestions for MOP and forms |
| July 2014 | Version 1 of MOP and forms completed |
| July 2014 | FIG meeting in Columbus |
| August 2014 | Prepare clinics and recruitment materials |
| August 2014 | Site Visits |
| August 2014 | Recruitment begins |
| July 2015 | Recruitment ends |
| September 2015 | DSMC meeting |
| September 2015 | Baseline manuscript submitted to Optometry and Vision Science |
| October 2015 | FIG meeting in Houston |
| November 2015 | Site Visits |
| September 2016 | DSMC meeting |

| | |
|----------------|---|

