| October 2016 | FIG meeting in Columbus |
| November 2016 | Site Visits |
| September 2017 | DSMC meeting |
| October 2017 | FIG meeting in Houston |
| November 2017 | Site Visits |
| August 2018 | Last subject completed |
| September 2018 | DSMC meeting |
| September 2018 | FIG meeting in Columbus |
| September 2018 | Submit primary outcome paper to JAMA (Aim 1) |
| November 2018 | Submit peripheral myopic defocus and myopia progression paper to IOVS (Aim 3) |
| February 2019 | Submit eye shape and contact lens correction paper to Vision Research (Aim 3) |

Chapter 7: Eligibility

In order to participate in the study, all subjects must meet the following criteria at Visit 1:

| | |
|------------------|---|
| Age | 7 to 11 years, inclusive, at baseline examination |
| Myopia | -0.75 to -5.00 D, inclusive, spherical component, cycloplegic autorefraction in each eye |
| Astigmatism | ≤1.00 DC, cycloplegic autorefraction in each eye |
| Anisometropia | ≤2.00 D, spherical component, cycloplegic autorefraction in each eye |
| Visual acuity | +0.1 logMAR or better best-corrected distance visual acuity in each eye AND +0.1 logMAR or better best-corrected, binocular, high contrast visual acuity at distance with +2.50 D add soft bifocal contact lenses on both eyes |
| Contact lens fit | The +2.50 D add soft bifocal contact lens must provide adequate movement and centration for continual wear |
| Ocular health | Free of eye disease or binocular vision problems (eg, strabismus, amblyopia, corneal disease, etc.) that may affect vision or contact lens wear |
| Systemic health | Free of systemic disease that may affect vision, vision development, or contact lens wear (eg, diabetes, Down syndrome, etc.) |
| Contact lens | By patient report, not more than one month of gas permeable, soft bifocal, or orthokeratology contact lens wear |
| Myopia control | By patient report, not more than one month of participation in myopia control with treatments including, but not limited to soft bifocal or orthokeratology contact lenses, atropine, bifocal spectacles |
| Medications | No chronic use of medications that may affect immunity, such as oral or ophthalmic corticosteroids |
| Participation | Agree to participate in the study for three years |

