For example, if a subject does not want to wear contact lenses, the subject should be asked why s/he does not want to wear contact lenses and every effort should be made to alleviate the reason for discontinuation. The subject and parent should be reminded of the importance of continuing in the study and reminded of the free comprehensive eye examinations and glasses throughout the study. At each follow-up visit, the subject should be asked if s/he would like to resume contact lens wear. If there are any irregularities in the case or if there are questions, contact the Study Chair.

Discontinuation

Subjects have the right to withdraw participation in a study at any time, but losses to follow-up may significantly affect the validity of the study. Every effort should be made to retain every subject for the entire study, including subjects who are difficult to schedule, subjects who are very demanding, and subjects whom you simply do not like.

If a subject moves from the area, the subject may be examined at the other clinic site or the Chair's Office may pay for the subject and one adult to fly to an appointment, one night's stay in a hotel, and ground transportation. The total reimbursement should not be greater than \$1350 per visit. This decision will be made on a person-by-person basis by the Clinic PI and Study Chair.

If a subject cannot be located, and the clinic site has exhausted all potential contacts, the Chair's Office will conduct a professional search using alternative resources. Contact the Chair's Office as soon as the clinic site determines that they are not able to locate the subject.

If a subject wishes to discontinue and all alternatives have been discussed, the examiner should ask the subject if he or she would come back for Visit 9 only. If the subject agrees to return for the last visit, then he or she is not a loss to follow-up, and the Discontinuation Form should not be completed. If the subject refuses to attend all of the remaining visits, the Discontinuation Form should be completed. At this time, complete the discontinuation section of the Study Completion Form in REDCap. Ask the subject if it would be acceptable to continue sending them information and see if it would be okay to call them before the last visit to determine whether the subject changed his or her mind.

Chapter 10: Informed Consent

Introduction

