The investigator should submit an abstract and a short description of the proposed paper including co-authors, data to be reported and timeline for drafts and submission. This information should be sent to the Study Chair. The Executive Committee is responsible for reviewing the proposal's merit and deciding if it should be a study publication. This review process is intended to ensure the quality of study publications and to refine the proposal. The Executive Committee is responsible for determining priorities (timeline and order of preparation) of proposed papers/presentations. Upon approval of the proposed paper/presentations, a detailed analysis plan and timetable are developed with the DCC.

The DCC is responsible for maintaining a database that tracks proposed and approved study publications and presentations. A list of approved study publications and presentations will be distributed to all investigators on a regular basis. Interested investigators are invited to contact the primary author to add their name to the writing group.

Should the workload associated with the preparation of papers exceed the resources of the DCC, it will be the responsibility of the DCC in conjunction with the Executive Committee to establish priorities. It will be the responsibility of the DCC to contact primary authors when timelines are not met. Major problems in the preparation of manuscripts are referred to the Executive Committee.

The primary author is responsible for coordinating all activities related to the writing and submission of papers and abstracts. This includes arranging conference calls, discussing analytic plans with the DCC, assigning writing responsibilities to co-authors, maintaining timeliness, determining the order of authorship, circulating drafts to co-authors, and circulating final drafts to the Executive Committee. Upon circulation of the draft, there will be a two-week period during which members can make comments about the paper.

If the focus of the paper changes as it moves from abstract to the manuscript stage, the primary author will notify the Study Chair in writing. The Study Chair will be responsible for insuring that the revised proposal receives appropriate review.

Each publication must acknowledge support as follows: "NIH U10 EY023204, 023206, 023208, 023210, P30 EY007551, and UL1 TR001070."

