The Study Chair will send a letter of approval with all manuscripts when they are submitted for publication. Some journals require that all individuals listed as member of the study group sign the copyright waiver form. If so, the writing committee will enlist the assistance of the Study Chair's Office to obtain these signatures.

Protocol for Submitting Publications

- Ideas for paper topics must be approved by the Executive Committee
- The Executive Committee will form a writing committee and determine a lead author
 - The lead author is typically the first author
 - Named authors include the writing committee members (generally 2 to 4, not including the Executive Committee) and the Executive Committee
- The writing committee, working with the Data Coordinating Center, should write Draft #1 of the paper.
- When all writing committee members are okay with Draft #1 of the paper, the paper should be submitted to the Study Chair
 - The Study Chair will add the Study Group listing to the manuscript and send the manuscript to the entire study group for review
 - The Study Chair and/or lead author will make edits to the manuscript
 - Responses must be received from *all* members of the Study Group
- Draft #2 will be sent to the DSMC for comments and approval
- Draft #3 will be submitted to the appropriate journal with the Study Chair as the corresponding author
- When reviews are received, the Study Chair and/or lead author will respond point-by-point to the reviews
- Draft #4 will be submitted to the journal, and this will continue until it is accepted or withdrawn
- When page proofs are received, the Study Chair, first author, and Data Coordinating Center Director will review the manuscript

Presentations

Oral presentations and abstracts to be printed must be approved in advance by the Executive Committee. No unpublished study results may be used for oral presentations, local or otherwise, unless a specific exception is granted by the Executive Committee. Study results include all data collected for the study. The above restrictions do not apply to local presentations of the design of the study, provided these presentations contain no unpublished study results. Such presentations are encouraged to stimulate subject recruitment.

Publications from Ancillary Studies

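### Does drafting the primary paper at 75% completion open an uncontrolled early look at results by arm?

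*Combined protocol and SAP*

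**What the plan says.** Chapter 6 (Timeline) schedules the paper: "When 75% of the subjects have completed the trial, a draft of the primary outcome manuscript will be written". The draft goes to the DSMC for approval. After the study is complete, "data will be finalized, the entire study group will provide comment prior to submission", and the DSMC then gives its final approval. Table 6-2 leaves about one month between the last subject (August 2018) and submission (September 2018).

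Chapter 31 gives the general procedure for all papers, under Protocol for Submitting Publications: "The writing committee, working with the Data Coordinating Center, should write Draft #1 of the paper". The Study Chair is then to "send the manuscript to the entire study group for review", and the next draft goes to the DSMC. The named authors include the Executive Committee, whose permanent members are the Study Chair, the Clinic PIs and the Data Coordinating Center (DCC) Director. Under Publications in the same chapter, once a proposed paper is approved, "a detailed analysis plan and timetable are developed with the DCC".

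Three other places bear on the point. Chapter 5 states the Aim 1 model: a repeated-measures ANCOVA of three groups by three annual visits, with baseline spherical equivalent as covariate. Chapter 12 has cycloplegic autorefraction done by a masked examiner. Chapter 33 has the DSMC set the monitoring plan and approve primary manuscripts for their scientific methods.

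**The concern.** Read quickly, Chapter 6 looks like an unplanned interim comparison. The paper is drafted while a sizeable group of children has yet to give the last primary measurement, and nothing says that the draft must be a shell. The people named as authors still run the trial. On paid travel for a child who has moved away, Chapter 9 says: "This decision will be made on a person-by-person basis by the Clinic PI and Study Chair". The Study Chair also takes questions about children who want to stop lens wear. Nor does the manual date the detailed analysis plan relative to the data.

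If the draft did hold results by arm, two things would be at stake: an even retention effort across arms before the last visits, and analysis choices made without sight of the answer.

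**Working it through.** **1. The plan's own sample size.** Chapter 5, Aim 3, gives 89 per group. A three-group F-test with means 0, 0.20 and 0.40 D, SD 0.85 D and alpha 0.05 reproduces this (power 0.805), total 267. The 10% allowance gives 267 × 1.10 = 293.7, so 294, with "98 children assigned to each treatment group".

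**2. Children outstanding at the trigger.**
- Completers: 0.75 × 294 = 220.5.
- With no loss: 294 − 220.5 = 73.5 outstanding.
- With the planned 10% loss already realised: 0.90 × 294 = 264.6, and 264.6 − 220.5 = 44.1 outstanding.

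**3. How much a comparison at that point would reveal.**
- Correlation with the final estimate: √(220.5/294) = 0.87 with no loss; √(220.5/264.6) = 0.91 with 10% loss.
- With about 73.5 children per arm and the Chapter 5 SD of 0.71 D, the unadjusted standard error of a difference in three-year change is 0.71 × √(2/73.5) = 0.117 D.
- The planned 0.65 D effect gives z = 0.65/0.117 ≈ 5.6. The 0.30 D step gives 0.30/0.117 ≈ 2.6.

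These figures show that a look would be informative. They do not show bias.

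**4. Bias through lens wear or switching.** Assume uniform accrual over 12 to 20 months (about 12 in Table 6-2, 20 in Chapter 34), linear progression, and complete loss of the effect in every outstanding child from the moment of the draft.
- No loss: the last quarter spans 3 to 5 months, so the mean remaining time is 1.5 to 2.5 months.
- 0.65 D over 36 months is 0.0181 D per month: 0.25 × 0.0181 × (1.5 to 2.5) = 0.007 to 0.011 D.
- 0.30 D over 36 months is 0.0083 D per month: 0.25 × 0.0083 × (1.5 to 2.5) = 0.003 to 0.005 D.
- 10% loss: the fraction is 44.1/264.6 = 0.167 and the mean remaining time 1.0 to 1.67 months, giving 0.001 to 0.005 D over both effects.

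The autorefractor step set in Chapter 19 is 0.12.

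**5. Bias through uneven retention.** The documents give no input here, so this is an assumed range. If k extra children are lost from one arm of 98, each s standard deviations from the mean in the same direction, that arm's mean moves by k × s × 0.71/(98 − k).
- k = 1, s = 0.5: 0.355/97 = 0.004 D, about 1% of 0.30 D.
- k = 5, s = 1: 3.55/93 = 0.038 D, about 13% of 0.30 D.

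One arm would have 73.5/3 = 24.5 or 44.1/3 = 14.7 children outstanding, so five extra losses are 20% to 34% of them. Chapter 5 cites retention of 98% to 100% and above 90% in comparable studies. The year 1 and 2 values, which are in the model, would shrink the shift further.

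**6. The two chapters side by side.** Chapter 6: DSMC sees the early draft, study completes, group comments, DSMC approves. Chapter 31: group reviews, then DSMC approves. Both put group comment before the DSMC's last approval. Chapter 31 covers every paper and sets no timing against data completion; Chapter 6 adds one early DSMC step for the primary paper. They can be followed together.

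**The case for a change.** The strongest case for a change is that silence is a poor safeguard when the authors still direct the trial. The manual knows this risk. Chapter 32 withholds treatment assignment from the Executive Committee when it rules on adverse events, and the Chapter 12 masking questions list having seen a study result as a reason for a guess. Chapter 5 names the model but does not settle how the two eyes are combined, how switched children are analysed or how missing visits are handled. Chapter 33 allows the Study Chair to sit on the DSMC ex officio, so sending the draft there is not a complete firewall. A line of text would cost almost nothing.

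What stands is that no written rule covers the draft's content, and that some analysis details are left to the later plan. What does not stand is the step from there to harm. Chapter 6 names only the DSMC as recipient of the early draft. Chapter 31 has the detailed plan follow approval of the paper's topic, which is also the first step before Draft #1. The conduct routes are narrow: paid travel concerns only children who move away, and a switch is a last resort to keep a child in the study. Unmasked examiners work with the lenses throughout in any case.

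**Conclusion.** No change is called for. This is a gap that a competent team fills sensibly: with about a month between last subject and submission, early drafting of background, methods and table layouts is the natural use of the time, and results go in once the data are final. The count of 44 to 74 outstanding children is right, and a comparison by arm at that point would be informative. But the manual does not plan one, and following it as written is not shown to give a worse result. The shift through wear or switching is 0.001 to 0.011 D under complete loss of effect, and at most 0.038 D through assumed retention losses, against planned effects of 0.30 and 0.65 D.

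This rests on reading the draft as a shell, on uniform accrual and linear progression, and on the plan's SD of 0.71 D. Part of the manual's opening chapters and the DSMC's monitoring plan are not in the available file, so a rule there cannot be excluded. Evidence that results by arm had in fact been circulated before the last Visit 9 would reopen the question.
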